### **7.3.6 *Subsequent Therapy***

A by-subject listing will be provided separately for subsequent systemic cancer therapy, on-treatment/subsequent radiotherapy and subsequent surgery.

### **7.3.7 *Physical Examination***

Subjects with abnormal baseline physical examination will be tabulated by examination criteria by HBV status and pooled for all treated participants.

The number and percentage of patients reporting physical examination results (Normal/Abnormal) will be presented per body system for all treated participants. In addition, shift table will be provided.

A by-subject listing will be provided.

### **7.3.8 Clinical Complaints**

Clinical complaints collected at screening will be summarized using count and percentage by CTC grade for all enrolled participants.

A by-subject listing will be provided.

### **7.3.9 Diagnostic and Medical Treatment Procedures**

A by-subject listing will be provided separately for diagnostic and medical treatment procedures.

### **7.3.10 Previous and Concomitant Prophylactic Vaccinations**

A by-subject listing will be provided separately for previous and concomitant prophylactic vaccinations.

## **7.4 Extent of Exposure**

Unless otherwise specified, the exposure data will be presented on treated participants by HBV status and pooled.

### **7.4.1 Administration of Study Therapy**

The following parameters will be summarized (descriptive statistics):

- Relative dose intensity (%) using the following categories: < 50%; 50 - < 70%; 70 - < 90%; 90 - < 110%; ≥ 110%.
- Number of doses received (summary statistics)
- Cumulative dose
- Duration of treatment: duration of treatment will be presented using a Kaplan-Meier curve whereby the last dose date will be the event date for subjects who are off study therapy. Subjects who are still on study therapy will be censored on their last dose date. Median duration of treatment and associated 95% CI will be provided.

A by-subject listing of dosing of study medication (record of study medication, infusion details, and dose change) and a listing of batch number will be also provided.

Below table summarizes the key parameters used to calculate dosing data.

**Table 7.4-1: Administration of Study Therapy: Definition of Parameters**

Nivolumab	
Dosing schedule per protocol	240 mg Q2 weeks
Cumulative Dose	Cumulative dose (mg) is sum of the doses (mg) administered to a subject during the treatment period
Relative dose intensity (%)	[Cumulative dose (mg)/((Last dose date - Start dose date + 14) 240 / 14)] x 100

**Table 7.4-1: Administration of Study Therapy: Definition of Parameters**

Nivolumab	
Duration of treatment	Last dose date - Start dose date +1

## **7.4.2 Modifications of Study Therapy**

### **7.4.2.1 Dose Delays**

A dose will be considered as actually delayed if the delay is exceeding 3 days (i.e., greater than or equal to 4 days from scheduled dosing date). The length of dose delay is defined as (duration of previous cycle in days - 14). The Dose delays will be divided into following categories: 4 - < 8 days, 8 - < 15 days, 15 - < 43, > 42 days. Reason for dose delay will be retrieved from CRF dosing pages.

The following parameters will be summarized by HBV status and overall:

- Number of dose delayed per subject, Length of Delay, and Reason for Dose Delay
- Number of subjects with at least one dose delayed along with reason for dose delay

### **7.4.2.2 Dose Modifications**

There will be no dose escalations or reductions of nivolumab allowed.

Nivolumab infusion can be interrupted and/or the IV infusion rate can be reduced. This information will be retrieved from CRF dosing pages.

The following parameters will be summarized by HBV status and overall:

- Number of subjects with at least one infusion with IV rate reduced along with the reason of the rate reduction
- Number of subjects with at least one dose infusion interrupted along with the reason for the interruptions and number of infusions interrupted per subject

A by subject listing of study drug administered will be provided. A batch listing number will be also provided.

In addition the following will be summarized:

- Number of subjects with at least one infusion with IV rate reduced along with the reason of the rate reduction
- Number of subjects with at least one dose infusion interrupted along with the reason for the interruptions and number of infusions interrupted per subject

A by subject listing of study drug administered will be provided. A batch listing number will be also provided.

### **7.4.3 Prior and Concomitant Medications**

Prior concomitant medication, defined as medications which are taken before the date of the first dose of study medication.

Concomitant medications, defined as medications other than study medications which are taken at any time on-treatment (i.e. on or after the first day of study therapy and within 100 days following the last dose of study therapy).

Prior and concomitant medications will be coded using the WHO Drug Dictionary. The following summary tables will be provided for all treated participants by HBV status and pooled:

- Prior concomitant medications (subjects with any concomitant medication, subjects by medication class and generic term)
- Concomitant medications (subjects with any concomitant medication, subjects by medication class and generic term)

A by-subject listing will accompany the tables.

## **7.5 Efficacy**

The Overall Survival (OS), Time to Treatment Failure (TTF), Progression-Free Survival (PFS) Objective Response Rate (ORR) and Best Overall Response (BOR) will be summarized using all treated participants by HBV status and pooled. The Duration of Response (DOR) and duration of SD will be summarized based on all response evaluable participants.

### **7.5.1 Primary Efficacy Analyses**

Not applicable.

### **7.5.2 Secondary Efficacy Analyses**

#### **7.5.2.1 Overall Survival (OS)**

Overall Survival (OS) is defined as the time from the first dosing date to the date of death. Participants without documentation of death will be censored on the last date the participant was known to be alive.

Time to event distribution will be estimated using Kaplan Meier techniques. Median OS along with 95% CI will be constructed based on a log-log transformed CI for the survivor function. OS Rates at fixed time points (6, 12, 18, and 24 months) will be derived from the Kaplan Meier estimate and corresponding confidence interval will be derived based on Greenwood formula for variance derivation and on log-log transformation applied on the survivor function.

The above methods for OS will be evaluated for pooled analysis and also in the following subgroups:

- Tumor Histology (Squamous and non-squamous)
- Tumor PD-L1 expression level (PD-L1 positive and PD-L1 negative protein expression)

- Infection Status (Non-HBV infected and HBV infected)
- Molecular Type (EGFR mutation, ALK positive and WT).

Overall survival estimate will be graphically displayed for overall and also for each subgroup analysis using the Kaplan-Meier technique.

#### **7.5.2.2 Time to Treatment Failure (TTF)**

Time to Treatment Failure (TTF) is defined as the minimum of the time from first dose date to disease progression (determined by investigator assessments using RECIST 1.1), death or last dose date if a subject progressed, died or discontinued from treatment for any reasons other than “maximum clinical benefit” and “administrative reasons by sponsor”.

Clinical progression date is considered as event for time to treatment failure only when treatment is discontinued due to clinical disease progression. For nivolumab subjects treated beyond RECIST 1.1 progression, the event will be at RECIST 1.1 progression date. TTF is censored at the last dose date for subjects who discontinued treatment (without RECIST 1.1 progression) due to maximum clinical benefit or administrative reason by sponsor. TTF is censored at the last dose date for subjects who continued on treatment without progression (per RECIST 1.1) or death at the time of the database lock.

Time to event distribution will be estimated using Kaplan Meier techniques. Median TTF along with 95% CI will be constructed based on a log-log transformed CI for the survivor function.

Sensitivity analysis will be conducted to censor TTF for discontinuations due to patient preference.

The above methods for TTF will be evaluated for all treated participants by HBV status and pooled. In addition, subgroup analysis will be performed in the following subgroups:

[figure not shown]
- Tumor Histology (Squamous and non-squamous)
- Tumor PD-L1 expression level (PD-L1 positive and PD-L1 negative protein expression)
- Infection Status (Non-HBV infected and HBV infected)
- Molecular Type (EGFR mutation, ALK positive and WT).

Time to Treatment Failure (TTF) will be graphically displayed for overall and also for each subgroup analysis using the Kaplan-Meier technique.

#### **7.5.2.3 Progression-Free Survival (PFS)**

Progression-Free Survival is defined as the time from first dose date to the date of the first documented tumor progression (per RECIST 1.1) or death due to any cause. Subjects who die without a reported prior progression will be considered to have progressed on the date of their death. Subjects who did not progress or die will be censored on the date of their last evaluable tumor assessment. Subjects who did not have any on study tumor assessments and did not die will be censored on their first dose date. Subjects who started any subsequent anti-cancer therapy

without a prior reported progression will be censored at the last evaluable tumor assessment prior to initiation of the subsequent anti-cancer therapy.

Time to event distribution will be estimated using Kaplan Meier techniques. Median PFS along with 95% CI will be constructed based on a log-log transformed CI for the survivor function.

The above methods for PFS will be evaluated for pooled analysis and also in the following subgroups:

- Tumor Histology (Squamous and non-squamous)
- Tumor PD-L1 expression level (PD-L1 positive and PD-L1 negative protein expression)
- Infection Status (Non-HBV infected and HBV infected)
- Molecular Type (EGFR mutation, ALK positive and WT).

Progression-Free Survival will be graphically displayed for overall and also for each subgroup analysis using the Kaplan-Meier technique.

#### **7.5.2.4 Objective Response Rate (ORR)**

Objective Response Rate (ORR) is defined as the proportion of all treated participants whose best overall response (BOR) from baseline is either a CR or PR per RECIST 1.1 criteria. BOR is determined by the best response designation recorded between the first dose date and the date of objectively documented progression or the date of subsequent anti-cancer therapy, whichever occurs first. For subjects without documented progression or subsequent anti-cancer therapy, all available response designations will contribute to the BOR determination. For subjects who continue nivolumab beyond progression, the BOR should be determined based on response designations recorded at the time of the initial RECIST 1.1 defined progression.

ORR will be summarized by binomial response rates and their corresponding two-sided 95% exact CIs using Clopper-Pearson method.

The above methods for ORR will be evaluated for pooled analysis and also in the following subgroups:

- Tumor Histology (Squamous and non-squamous)
- Tumor PD-L1 expression level (PD-L1 positive and PD-L1 negative protein expression)
- Infection Status (Non-HBV infected and HBV infected)
- Molecular Type (EGFR mutation, ALK positive and WT).

Objective Response Rate (ORR) will be graphically displayed for overall and also for each subgroup analysis using the Kaplan-Meier technique.

#### **7.5.2.5 Duration of Response (DOR)**

Duration of Response (DOR) is defined as the time between the date of first confirmed response to the date of the first documented tumor progression (per RECIST 1.1) or death due to any cause. Subjects who neither progress nor die will be censored on the date of their last evaluable tumor assessment. The Subjects who started any subsequent anti-cancer therapy (excluding on-treatment palliative radiotherapy of non-target bone lesions, skin lesions or CNS lesions) without a prior reported progression will be censored at the last evaluable tumor assessment prior to or on the date of initiation of the subsequent anti-cancer therapy. The censoring algorithm for DOR will be the same as used for PFS definition. This endpoint will only be evaluated for participants with BOR of CR or PR.

The DOR will be summarized for all treated participants who achieve confirmed PR or CR using the Kaplan-Meier (KM) product-limit method. Median values of DOR, along with two-sided 95% CI using Brookmeyer and Crowley method, will also be calculated.

Duration of Stable Disease will also be evaluated for subjects with SD as best response. Duration of SD is defined as the time between the date of first dose to the date of the first documented tumor progression (per RECIST 1.1) as assessed by the investigator, or death due to any cause, whichever occurs first. Censoring rules will be the same as for DOR analysis.

The above methods for DOR and duration of SD will be evaluated for pooled analysis and also in the following subgroups:

- Tumor Histology (Squamous and non-squamous)
- Tumor PD-L1 expression level (PD-L1 positive and PD-L1 negative protein expression)
- Infection Status (Non-HBV infected and HBV infected)
- Molecular Type (EGFR mutation, ALK positive and WT).

The DOR will be graphically displayed for overall and also for each subgroup analysis using the Kaplan-Meier technique.

A by-subject listing will be provided for OS, TTF, PFS, ORR and DOR.

## **7.6 Safety**

All the safety analysis will be performed for all treated participants by HBV status and pooled. Analysis windows/analysis visits are outlined in [Appendix 2](#).

### **7.6.1 Deaths**

See Core Safety SAP.

### **7.6.2 Serious Adverse Events**

See Core Safety SAP.

### **7.6.3 Adverse Events Leading to Discontinuation of Study Therapy**

See Core Safety SAP.

### **7.6.4 Adverse Events Leading to Dose Modification**

See Core Safety SAP.

### **7.6.5 Adverse Events**

See Core Safety SAP.

### **7.6.6 Select Adverse Events**

See Core Safety SAP.

### **7.6.7 Multiple Events**

See Core Safety SAP.

### **7.6.8      *Other Events of Special Interest***

See Core Safety SAP.

### **7.6.9      *Immune Mediated Adverse Events***

See Core Safety SAP.

### **7.6.10     *Clinical Laboratory Evaluations***

Laboratory evaluations will be reported using both the US conventional unit and Standard International (SI) unit.

The analysis population for each laboratory test is restricted to treated participants who underwent that laboratory test. Laboratory tests (in addition to the tests specified below) with CTC criteria collected in the specific studies may also be included in the summaries. In addition, baseline laboratory results will be summarized using descriptive statistics for all treated participants.

#### **7.6.10.1    *Hematology***

See Core Safety SAP.

#### **7.6.10.2    *Serum Chemistry***

See Core Safety SAP.

#### **7.6.10.3    *Electrolytes***

See Core Safety SAP.

#### **7.6.10.4    *Abnormal Thyroid Function Test***

See Core Safety SAP.

#### **7.6.10.5    *Abnormal Hepatic Function Test***

See Core Safety SAP.

### **7.6.11     *Vital Signs and Pulse Oximetry***

See Core Safety SAP.

### **7.6.12     *Electrocardiogram***

Descriptive summary will be provided for electrocardiogram parameters include (Heart Rate (bpm), PR Interval (msec), QRS width (msec), QT Interval (msec), QTc Bazett's (msec) and QTc

Fridericia's (msec)) by visit for all treated participants for observed values and changes from baseline for all treated participants by HBV status and pooled.

The overall ECG interpretation will be summarized by presenting the number and percentage of subjects with “Normal” and “Abnormal” by scheduled time-point. In addition, shift table will be provided to see the significant changes in ECG parameters. Also, abnormal findings will be listed separately.

By subject listing will be provided.

#### **7.6.13    ECOG Performance Status**

Summaries of ECOG performance will be provided for all treated participants by HBV status and pooled. In addition, continuous variable summary will be provided using descriptive statistics. A shift table will be provided to see the significant changes from baseline to post-baseline visits.

A by-subject listing of ECOG will be provided.

Classification of ECOG performance status is provided in Table 7.6-13.

**Table 7.6-13:                    ECOG PERFORMANCE STATUS**

ECOG PERFORMANCE STATUS	
Grade	ECOG
0	Fully active, able to carry on all pre-disease performance without restriction
1	Restricted in physically strenuous activity but ambulatory and able to carry out work of a light or sedentary nature, e.g., light house work, office work
2	Ambulatory and capable of all self-care but unable to carry out any work activities. Up and about more than 50% of waking hours
3	Capable of only limited self-care, confined to bed or chair more than 50% of waking hours
4	Completely disabled. Cannot carry on any self-care. Totally confined to bed or chair
5	Dead

#### **7.6.14    Pregnancy Testing**

By-subject listing of pregnancy tests results will be provided for all treated female subjects.

### **7.7                    Pharmacokinetics**

Not applicable

## **7.8 Other Analyses**

### **7.8.1 Biomarkers**

The biomarker analysis will be performed for the Biomarker Subjects Population, which is defined as all treated participants with available biomarker data. Analyses for PD-L1 are described below.

#### **Distribution of PD-L1 Expression**

The following statistics of PD-L1 expression will be produced for pooled analysis and by tumor histology and molecular genotype:

- Listing of all PD-L1 immunohistochemistry (IHC) data
- Summary of tumor specimen acquisition and characteristics, all treated participants by HBV status and pooled.
- Summary statistics of PD-L1 expression with quantifiable PD-L1 expression
- 2 by 2 contingency table of PD-L1 status by response status (yes CR or PR; No SD or PD or unknown).

### **7.8.2 Outcomes Research Analyses**

#### **LCSS (Lung Cancer Symptom Scale)**

The LCSS completion rates, defined as the proportion of questionnaires actually received out of the expected number will be calculated and summarized at each assessment point for all treated participants by HBV status and pooled. The baseline and change from baseline of the LCSS scores at each assessment point will be summarized using descriptive statistics.

The disease-related symptom deterioration rate at week 12 and week 24 as measured by LCSS and its corresponding 95% CI will also be calculated by Clopper-Pearson method.

All summaries for LCSS will be done for all treated participants by HBV status and pooled. In addition, subgroup analysis will be performed by tumor histology (SQ or NSQ), by PD-L1 expression (PD-L1 negative or PD-L1 positive), by infection status (HBV infection or non-HBV infection), and by molecular type (EGFR mutation, ALK translocation, or WT).

By subject listing will be provided for all treated participants.

#### **EuroQoL EQ-5D**

The EQ-5D completion rates, defined as the proportion of questionnaires actually received out of the expected number will be calculated and summarized at each assessment point for all treated participants by HBV status and pooled. The EQ-5D (with two essential components: the EQ-5D descriptive system and the EQ visual analogue scale (EQ VAS)) will be used to assess the subject's overall health status.

Proportion of subjects reporting problems for the 5 EQ-5D dimensions at each assessment time point will be summarized by level of problem. Percentages will be based on number of subjects

assessed at assessment time point. Subject's overall health state on a visual analog scale (EQ-VAS) at each assessment time point will be summarized using descriptive statistics (N, mean, SD, median, 25th and 75th percentiles).

The N3 model based on ordinary least square regression at the aggregate level was used to generate a Chinese general population-based three level EuroQol five-dimensions (EQ-5D-3L) social value set. Value set for Chinese population will be used to get utility values for each individual. The baseline and change from baseline of the EQ-5D scores at each assessment point will be summarized using descriptive statistics.

The preference scores are calculated from the following algorithm,

Score = 1 - Constant - MOx - SCx - UAx - PDx - ADx - N3

[figure not shown]
MO, SC, UA, PD and AD are the five dimensions (mobility, self-care, usual activities, pain/discomfort, and anxiety/depression). x is the three levels for each dimension (1 = no problems, 2 = some/ moderate problems, and 3 = extreme problems).

Coefficient generated from N3 model is provided in below table

	Value for each dimension (x)	Coefficient
Constant		0.039
MO	1	0
	2	0.099
	3	0.246
SC	1	0
	2	0.105
	3	0.208
UA	1	0
	2	0.074
	3	0.193
PD	1	0
	2	0.092
	3	0.236
AD	1	0
	2	0.086
	3	0.205
N3		0.022

All summaries for EQ-5D will be done for all treated participants for pooled analysis and also by tumor histology (SQ or NSQ), by PD-L1 expression (PD-L1 negative or PD-L1 positive), by infection status (HBV infection or non-HBV infection), and by molecular type (EGFR mutation, ALK translocation, or WT).

By subject listing will be provided for all treated participants.

## **8 CONVENTIONS**

The following conventions may be used for imputing partial dates for analyses requiring dates:  
For death dates, the following conventions will be used for imputing partial dates:

- If only the day of the month is missing, the 1st of the month will be used to replace the missing day. The imputed date will be compared to the last known date alive and the maximum will be considered as the death date.
- If the month or the year is missing, the death date will be imputed as the last known date alive
- If the date is completely missing but the reason for death is present the death date will be imputed as the last known date alive

For date of progression, the following conventions will be used for imputing partial dates:

- If only the day of the month is missing, the 1st of the month will be used to replace the missing day.
- If the day and month are missing or a date is completely missing, it will be considered as missing.

In cases where the date of death is present and complete, the imputed progression date will be compared to the date of death. The minimum of the imputed progression date and date of death will be considered as the date of progression.

For missing and partial adverse event onset dates, imputation will be performed using the Adverse Event Domain Requirements Specification.

For missing and partial adverse event resolution dates, imputation will be performed as follows (these conventions may change):

- If only the day of the month is missing, the last day of the month will be used to replace the missing day
- If the day and month are missing or a date is completely missing, it will be considered as missing.

Missing and partial non-study medication domain dates will be imputed using the derivation algorithm described in 4.3.3 of BMS Non-Study Medication Domain Requirements Specification.

For other partial/missing dates, the following conventions may be used:

- If only the day of the month is missing, the 15th of the month will be used to replace the missing day.
- If both the day and the month are missing, “July 1” will be used to replace the missing information.
- If a date is completely missing, it will be considered as missing.

The following conversion factors will be used to convert days to months or years: 1 month 30.4375 days and 1 year 365.25 days.

Duration (e.g. time from first diagnosis to first dosing date, duration of response, and time to response) will be calculated as follows:

Duration (Last date - first date + 1)

For the LCSS symptom burden index, values will be imputed for missing symptom-specific items by using values equal to the average of the nonmissing symptom-specific items if at least half the items are completed. If less than half of the symptom-specific items are completed data will be treated as missing. For the LCSS three item global index, missing data will not be imputed to minimize bias. If the score for one item is missing, the index score will be treated as missing.

For the EQ-5D, no adjustment will be made for missing data when scoring the EQ-5D index or the EQ-5D VAS.

All statistical analyses will be carried out using SAS (Statistical Analysis System software, SAS Institute, North Carolina, USA) unless otherwise noted.

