### **8.3 Lost to Follow-Up**

- All reasonable efforts must be made to locate participants to determine and report their ongoing status. This includes follow-up with persons authorized by the participant.
- Lost to follow-up is defined by the inability to reach the participant after a minimum of **three** documented phone calls, faxes, or emails as well as lack of response by participant to one registered mail letter. All attempts should be documented in the participant's medical records.
- If it is determined that the participant has died, the site will use permissible local methods to obtain date and cause of death.
- If investigator's use of third-party representative to assist in the follow-up portion of the study has been included in the participant's informed consent, then the investigator may use a Sponsor retained third-party representative to assist site staff with obtaining participant's contact information or other public vital status data necessary to complete the follow-up portion of the study.
- The site staff and representative will consult publicly available sources, such as public health registries and databases, in order to obtain updated contact information.
- If after all attempts, the participant remains lost to follow-up, then the last known alive date as determined by the investigator should be reported and documented in the participant's medical records.

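### Three date-imputation rules in SAP section 8 can give progression or death dates that the participant's own records contradict, or leave a known progression with no event date

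*SAP*

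**What the plan says.** SAP section 8 gives separate lists for partial death dates and partial progression dates. The section opens permissively, but the sentences introducing these two lists are mandatory.

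- **Progression, day missing:** "If only the day of the month is missing, the 1st of the month will be used to replace the missing day". An upper bound follows: "In cases where the date of death is present and complete, the imputed progression date will be compared to the date of death", and then "The minimum of the imputed progression date and date of death will be considered as the date of progression". No lower bound is given.
- **Progression, day and month missing, or no date:** "If the day and month are missing or a date is completely missing, it will be considered as missing". Whether the event still counts is not stated.
- **Death, day missing:** the 1st of the month again, but with a floor: "The imputed date will be compared to the last known date alive and the maximum will be considered as the death date".
- **Death, month or year missing:** "If the month or the year is missing, the death date will be imputed as the last known date alive".
- **Death, no date at all:** kept as an event at the last date known alive, provided a reason for death is recorded.

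For PFS, SAP 7.5.2.3 says: "Subjects who did not progress or die will be censored on the date of their last evaluable tumor assessment". SAP 7.5.2.5 applies the same censoring algorithm to DOR. SAP 7.5.2.2 also uses a clinical progression date as a TTF event when treatment stops for that reason.

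**The concern.** The lists treat similar problems differently. The day-missing death rule is protected against contradicting a record already held; the day-missing progression rule is not. An undated death with a reason is kept as an event, while an undated progression is left without a date and without a stated status. A known month of death is used when the day is missing, but a known year is discarded when the month is missing.

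The errors run in different directions. A progression dated too early shortens PFS, DOR or TTF and can even give a negative time. A known progressor who is censored lengthens PFS and DOR. A death placed in an earlier year than the recorded one shortens OS, which SAP 2.1 calls a key endpoint.

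**Working it through.** The plan states no figure for these rules, so there is none to reproduce. The check applies each rule to dates.

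**Inputs from the documents**
- Scans (Protocol Table 2-2): first at 8 weeks ± 7 days, so no earlier than day 56 − 7 = 49. Then every 8 weeks ± 1 week, so at least 56 − 7 − 7 = 42 days apart. After week 48, every 12 weeks.
- Survival contact (Protocol Table 2-3, SAP Appendix 1): about every 12 weeks.
- Duration (SAP 8): last date − first date + 1.
- About 400 treated.

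**Assumptions:** event dates uniform over a 365-day year; gap from last contact to death uniform from 0 to 83 days; 1 to 10% of progression dates affected; true median PFS 2 to 6 months.

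**Rule 1, progression with day missing**

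*Scheduled scans.* Imputation moves a date back by at most 30 days. Since 30 < 42 and 30 < 49, it cannot reach the previous scan or first dose. A simulation of 100,000 progressions agrees: 0% contradicted, mean shift −14.8 days.

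*Off-schedule records.* Suppose progression falls g days after a record of no progression. The imputed date is on or before that record whenever the true day of the month exceeds g. For g up to 28 the share is 1 − 12g/365:

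| g (days) | Formula | Simulated |
|---|---|---|
| 1 | 96.7% | 97% |
| 7 | 77.0% | 77% |
| 14 | 54.0% | 54% |
| 21 | 31.0% | 31% |
| 28 | 7.9% | 8% |
| 35 or more | 0% | 0% |

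The protocol creates such records. Section 7.7.1.2 asks for evaluation before palliative local therapy, and Appendix 6 section 2.3.4 asks for verification of equivocal progression. Example: such an evaluation on 3 May shows no progression, the scheduled scan on 28 May does, and the day is lost. The imputed date is 1 May.

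*Before the first scheduled scan.* First dose 5 March, progression in March with the day unknown: imputed 1 March, and time = 1 − 5 + 1 = −3 days. A clinical progression date used for TTF can do the same.

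**Rule 2, progression without a usable date**

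A Kaplan-Meier event needs a date. With none, and no death, the only operative rule left is censoring at the last evaluable assessment. In simulated trials of 400 (exponential event times, affected participants censored at the previous scheduled scan), median PFS rose by about 0.2 to 1.4 days with 1% affected, and by up to about 11 days with 10% affected and a true median of 6 months.

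**Rule 3, death with year known and month missing**

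Example: last known alive 15 November 2018, death recorded only as 2019. The rule returns 15 November 2018. The earliest date consistent with the record is 1 January 2019, which is 15 + 31 + 1 = 47 days later, so OS is at least 47 days short.

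Share in the wrong year = mean gap / 365 = 41.5/365 = 11.4% (simulated 11.5%). For 4-week contact the simulated share is 3.8%, and for a 180-day interval about 24%. The simulated mean OS shift with 12-week contact is −41 days; a floor at 1 January makes it −38 days and removes every wrong-year date.

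**Rules that pass:** the day-missing death rule produced no contradictions. The minimum with death changes nothing unless the recorded progression month is later than the death month.

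**The case against.** The strongest case on the other side is that little here is an error in practice, and much of it stands.

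- A reader might infer that the minimum with the death date is the fault. It is not; it is a correct upper bound, and what is missing is a lower one.
- A reader might infer that the SAP drops undated progressions. It does not say so. The date is set to missing, a later death still counts for PFS and DOR, and the PFS censoring sentence is written for those who did not progress. Event status is unspecified, and censoring is the likely practical result rather than a stated rule.
- A reader might take the mean shift of about 15 days as the size of the Rule 1 defect. That shift comes from the 1st-of-month convention, which is ordinary and which the fix keeps. It moves median PFS by about 0 to −2.6 days with 1 to 10% affected. The missing floor matters only for off-schedule or early progressions.
- Verification of equivocal progression is partly covered already: a confirmed progression takes the initial scan date. Only an unconfirmed one leaves a non-progression record that a later imputed date can contradict.
- For deaths, three-monthly contact limits most errors, and Protocol 8.3 says that "the site will use permissible local methods to obtain date and cause of death". For someone lost to follow-up the error can still be large. Last contact by 31 March and death recorded only as the following year gives at least 276 days, about 9 months, but that is an extreme case.

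None of this answers the remaining point. Followed as written, the rules can contradict a record in hand or leave a known event without a date, and neighbouring rules in the same section avoid this.

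**Conclusion.** The point holds as a minor one. Rule 1 can place progression before first dose, or on or before a same-month non-progression record, but only through off-schedule evaluations, progression before the first scheduled scan, or clinical progression dates used for TTF. Rule 2 leaves a documented progression with no event date, so a living participant would in practice be censored, biasing PFS and DOR upward. Rule 3 can put a death in an earlier year than the recorded one, for about 11.5% of such deaths under 12-week contact and a uniform gap.

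The documents do not support the broader reading that PFS, DOR and OS are wrong for everyone with a partial date: most imputed dates are approximate, not contradicted. The number of partial dates is not given. At an assumed 1 to 2% of 400 it would be 4 to 8 participants, and the effect on medians is likely small. The endpoints concerned are secondary and descriptive, with no hypothesis test.

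**What to change.** Amend three sentences in SAP section 8 before database lock:

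1. **Progression, day missing:** use the latest of the 1st of the recorded month, the first dose date, and the day after the last non-progression assessment that precedes the recorded progression. Do not go beyond the end of the recorded month; then take the minimum with the death date. The restriction to preceding assessments is needed because Protocol 7.4.4 and 9.1.1 continue scanning in participants treated beyond progression, and a later scan must not push the date forward. In the March example this gives 5 March and a time of 1 day; in the May example, 4 May.
2. **Progression without a usable date:** state that a documented progression remains an event, dated to the assessment or visit at which it was recorded. SAP Appendix 2 already assigns undated observations by the visit code of the collection instrument.
3. **Death, year known and month missing:** use the later of 1 January of that year and the last date known alive.

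The cost is three sentences and minor programming, with no new data. The day-missing death rule and the cap at death can stay as they are.
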